There is a considerable body of literature that suggests that completeness of resection is a positive factor for longer term survival in individuals with malignant glioma. Unfortunately, it is often difficult to completely remove a malignant brain tumor because during surgery it is sometimes very difficult to distinguish tumor from normal brain. It would be very helpful if there would be some way to help the neurosurgeon make this distinction. Malignant glioma tumor cells (more so than normal cells) contain the biosynthetic pathways to produce protoporphorin from a naturally occurring amino acid, 5-aminolevulinic acid (5-ALA). Protoporphorin is the immediate precursor to hemoglobin and is fluorescent under deep blue light. When exogenous 5-ALA is provided at increased concentration, protoporphorin concentration in the malignant cell increases at a rate far greater than normal brain cells and renders the malignant cell fluorescent red under blue light. This feature distinguishes the tumor cells from normal cells intraoperatively and facilitates complete resection.

Recent studies in Germany have confirmed the utility of pre-operative oral 5-ALA and intraoperative brain tumor fluorescence in aiding the resection of malignant brain tumors. These studies have led to the approval of oral 5-ALA for this indication by the European Medicines Agency, but it has not been approved for this indication by the United States FDA. This proposal is a phase 1 and phase 2 trial that will hopefully lead to FDA approval of oral 5-ALA for intraoperative visualization of malignant brain tumors.

In the phase 1 part of this proposed study, a minimum of three to a maximum of *18 patients will be administered oral 5-ALA two-three hours prior to surgery in cohorts of three at five escalating doses of 5-ALA (10, 20, 30, 40, or 50 mg/kg).

Dose-Escalation Schedule				
Dose Level	Dose of 5-ALA			
Level 1	10 mg/kg			
Level 2	20 mg/kg			
Level 3	30 mg/kg			
Level 4	40 mg/kg			
Level 5	50 mg/kg			

(*Due to four patients receiving 40mg/kg rather than three, 19 total patients will be studied in phase 1. Protocol deviation approved by IRB on 17 Oct 2013.)

The following data will be collected:

- Dose-limiting toxicity data.
- Tumor fluorescence assessed by neurosurgeon (0 to +++) in three distinct areas of fluorescence (Strong fluorescence, Weak fluorescence, No fluorescence).
- Tumor density from biopsies obtained by the neurosurgeon in the same three distinct areas of fluorescence and assessed by neuropathology (Solid tumor, Tumor mixed infiltrating normal brain, No tumor).

2

- Neurosurgeon's intra-operative estimate of residual tumor.
- Neuroradiologist's estimate of post-operative residual tumor on MRI.

This trial will evaluate:

The toxicity of a single dose of oral 5-ALA given pre-operatively.

- The sensitivity and specificity of 5-ALA Protoporphyrin IX (Pp IX) as an intraoperative fluorescent detection agent and aid for resection of tumor tissue remaining in the walls of the resection cavity of primary and recurrent malignant brain tumors.
- The relationship of the neurosurgeon's estimate of the extent of malignant glioma resection (as guided by tumor fluorescence) to the actual extent of resection determined by post-operative imaging.

Following completion of the phase 1 portion of this trial, an additional 16 subjects will be entered at the recommended phase 2 dose level in order to further define the above parameters at the recommended phase 2 dose level.

THE REMAINDER OF THIS PAGE IS LEFT INTENTIONALLY BLANK.

IRB NUMBER: 12-135

TABLE OF CONTENTS

SC	HEMA		Page 2
1	OR IF	CTIVES	6
••	1.1	Primary Objectives	
		Timory Objectives	
2.	BACK	GROUND	6
	2.1	5-ALA	
	2.2	Brain Tumors	
	2.3	Rationale	
	2.4	Correlative Studies Background	
			
3.	PATIE	NT SELECTION	15
	3.1	Eligibility Criteria	15
	3.2	Exclusion Criteria	
	3.3	Inclusion of Women and Minorities	16
4.	TREA	TMENT PLAN	16
	4.1	5-ALA Administration	16
	4.2	Definition of Dose-Limiting Toxicity	19
	4.3	Supportive Care Guidelines	
	4.4	Duration of Therapy	20
	4.5	Duration of Follow-up	20
	4.6	Criteria for Removal from Study	21
5.	DOSIN	IG DELAYS/DOSE MODIFICATIONS	21
6.	ADVE	RSE EVENTS: LIST AND REPORTING REQUIREMENTS	21
٠.	6.1	Comprehensive Adverse Events and Potential Risks List (CAEPR)	
	6.2	Adverse Events Characteristics	
	6.3	Expedited Adverse Event Reporting	
	6.4	Routine Adverse Event Reporting	
	• • •		
7.	PHAR	MACEUTICAL INFORMATION	22
	7.1	Drug (5-ALA)	
	7.2	Drug Availability	
	7.3	Drug Ordering	
	7.4	Drug Accountability	
8.	CORR	ELATIVE/SPECIAL STUDIES	22
	8.1	Assessment of Visual Tumor Discrimination	
9.	STUD	Y CALENDAR	23
10	MEAS	UREMENT OF EFFECT	24
	10.1	Definitions.	24
	10.2	Guidelines for Evaluation of Measurable Disease	
	10.3	Confirmatory Measurement/Duration of Response	
		·	
11	. REGU	LATORY AND REPORTING REQUIREMENTS	24

1. OBJECTIVES

- 1.1 Primary Objectives:
 - 1.1.1 Establish a safe dose for oral 5-ALA administration.
 - 1.1.2 Determine the sensitivity and specificity of 5-ALA mediated fluorescence for malignant glioma tissue in the brain.
 - 1.1.3 Compare the neurosurgeon's intra-operative estimate of the extent of malignant glioma resection (as guided by tumor fluorescence) with the actual extent of resection determined by post-operative imaging.

2 BACKGROUND

2.1 Aminolevulinic Acid (5-ALA)

Aminolevulinic acid (also known as ALA, 5-ALA, 5-Aminolevulinic acid, D-Aminolevulinic acid, dALA or δ ALA) is a naturally occurring substance that is found in all organisms, including humans, and is necessary for part of the basic metabolic life processes (*Figure 1*). It is the first compound in the porphyrin synthesis pathway, the pathway that leads to hemoglobin in mammals and chlorophyll in plants. In non-photosynthetic eukaryotes such as animals, insects, fungi, and protozoa, as well as the α -proteobacteria group of bacteria, it is produced by the enzyme 5-ALA synthase, from glycine and succinyl CoA. This reaction is known as the Shemin pathway.²³

Figure 1. 5-Aminolevulinic acid (C5H9NO3, MW 167.6)

Approximately 350 mg of 5-ALA is synthesized in humans each day for endogenous heme production. Administration of exogenous 5-ALA results in the production of high intracellular (mitochondrial) concentrations of Protoporphyrin IX (Pp IX). 5-ALA (and other porphyrins) and Pp IX are excreted in the urine and the stool (via bile), respectively. PpIX has properties of strong fluorescence and can also act as a photosensitizing agent for photodynamic therapy - resulting in cell death.

6

2.1.1 Pharmacology

The metabolism of 5-ALA is the first step in the biochemical pathway resulting in heme synthesis. 5-ALA is not fluorescent or a photosensitizer, but rather a metabolic precursor of PpIX, which is fluorescent and a photosensitizer. The synthesis of 5-ALA is normally tightly controlled by feedback inhibition of the enzyme, 5-ALA synthetase, presumably by intracellular heme levels. 5-ALA, when provided to the cell, bypasses this control point and results in the accumulation of PpIX, which is converted into heme by ferrochelatase through the addition of iron to the PpIX nucleus (see Figure 2).

[figure not shown]

Figure 2. ALA synthase, the first enzyme of the heme biosynthetic pathway, catalyzes the condensation of glycine and succinyl coenzyme A to form ALA. This enzyme is localized in the inner membrane of mitochondria. Separate genes encode erythroid and nonerythroid ALA synthases. ALA dehydratase, a cytosolic enzyme, converts two molecules of ALA into a monopyrrole, porphobilinogen (PBG), with the removal of two molecules of water. PBG deaminase catalyzes the condensation of four molecules of PBG to yield a linear tetrapyrrole, hydroxymethylbilane (HMB). Uroporphyrinogen III cosynthase catalyzes the formation of uroporphyrinogen III from HMB. Uroporphyrinogen decarboxylase, a cytosolic enzyme, catalyzes four sequential decarboxylations of the carboxymethyl side chains in uroporphyrinogen III (an octacarboxyl porphyrin) to yield heptacarboxyl porphyrin, hexacarboxyl porphyrin, pentacarboxyl porphyrin, and, finally, coproporphyrinogen III (a tetracarboxyl porphyrin). This enzyme can also metabolize uroporphyrinogen I to coproporphyrinogen I. Coproporphyrinogen oxidase, a mitochondrial enzyme in mammalian cells, catalyzes the removal of the carboxyl group and two hydrogens from the proprionic groups of pyrrolerings A and B of coproporphyrinogen III to form vinyl groups at these positions, forming protoporphyrinogen. This enzyme is unable to metabolize coproporphyrinogen I. Protoporphyrinogen oxidase mediates the oxidation of protoporphyrinogen IX to protoporphyrin IX, catalyzing the removal of six hydrogen atoms from the porphyrinogen nucleus. Protoporphyrin, the final intermediate in the pathway, is the only intermediate that is an oxidized porphyrin. Porphyrins in the oxidized state are reddish and fluoresce when exposed to long-wave ultraviolet light. Porphyrinogens that leak into extracellular fluid undergo auto-oxidation and are excreted primarily as porphyrins.

2.1.2 Pharmacodynamics of 5-ALA

When exogenous 5-ALA is administered either orally, intravenously or topically, it is taken up by the cells and metabolized in the pathway described, resulting in a large temporary accumulation of PpIX in the mitochondria. Exogenous 5-ALA induces elevated PpIX levels in most (but not all) tissues that line body surfaces or body cavities. It can be shown that PpIX preferentially accumulates in the mucosa of the rat colon, but to a much lesser

extent in the submucosa and muscle layers.3 Mucosal selectivity occurs for other organs (stomach, bladder) in vivo when 5-ALA is administered either intravenously or orally. 17 Tissues that show no 5-ALA-induced PpIX include muscle (striated, smooth and cardiac), dermis, blood vessels, mature erythrocytes and most (but not all) other tissues of mesodermal origin.¹⁹ However, since most of these mesodermal tissues have multiple components. a more detailed examination might reveal that a minority component in some tissues does in fact show a measurable degree of 5-ALA induced PpIX.

Malignant tissues usually accumulate more PpIX than do corresponding normal tissues from which they are derived. Increased PpIX accumulation can be found in many malignant cell lines, as compared to their non-malignant counterparts.4 A number of studies have indicated that exogenous 5-ALA results in a selective and preferential accumulation of PpIX in diseased or neoplastic cells more than in normal cells. In terms of tumor-to-normal tissue (T/N) ratio of formed PpIX, 5-ALA-mediated accumulation of PpIX contrasts of 10:1 up to 90:1 have been reported depending on the pathologic condition, 5-ALA drug dose, and time post-administration.1

There are also certain non-malignant but altered tissues that show enhanced PpIX production in comparison to cells in their normal state. Examples of these tissues are psoriatic, actinic keratotic and pre-keratotic lesions. Thus, while an enhancement of 5-ALA induced PpIX accumulation is not specific for malignant tissues, in general it does indicate the presence of some abnormality.

It is unclear what the exact mechanism is for the selective accumulation of PpIX in neoplastic tissue over normal tissue when presented with exogenous 5-ALA. It is clear, however, that this selective accumulation is not due to differences in the cellular uptake of 5-ALA.¹³ Whatever the mechanism, it is obvious from a kinetic point of view that the slowest step between the uptake of 5-ALA and formation of PpIX must be considerably faster than the transformation of PpIX into heme to attain a larger accumulation of PpIX and this occurs more robustly in neoplastic cells than in normal cells.¹⁴

PpIX is strongly fluorescent when activated by light at the far blue end of the visible spectrum in the Soret band (400nm). It emits a characteristic fluorescence spectrum with two prominent peaks in the red at 630nm and 700nm. This property has been used by various surgical specialties to help identify tumor for resection and to evaluate the extent of resection. Specifically for neurosurgery an oral form of 5-ALA (Gliolan, Medac GmbH, Wedel, Germany) has been approved by the European Medicines Agency in September 2007 for for visualisation of malignant tissue during surgery for malignant glioma (WHO grade III and IV)

(http://www.emea.europa.eu/pdfs/human/press/pr/42748007en.pdf). The results of MC-ALS.8-I/GLI Phase I/II and subsequent Phase III trials in Europe have been summarized in a number of recent papers by Walter Stummer M.D. and his colleagues.^{28,29,31,33} The European Medicines Agency comments can be found at:

http://www.emea.europa.eu/humandocs/PDFs/EPAR/gliolan/H-744-en6.pdf (also see section 2.3) and the package insert for Gliolan can be found at http://www.emea.europa.eu/humandocs/PDFs/EPAR/gliolan/H-744-PI-en.pdf

The accumulation and fluorescence of PpIX in tumor cells is not the only biological property of this 5-ALA metabolite. Photodynamic therapy of tumors is also possible with the accumulation of PpIX in tumor cells. Photodynamic therapy involves the photoactivation of a photosensitizer which when activated will kill tumor cells. The fundamental building block of most redabsorbing, naturally occurring photosensitizers is 5-ALA. These sensitizers including PpIX are can cause cell death when exposed to light of certain frequencies. PpIX has the ability to absorb a photon of visible light and then transfer most of this absorbed energy to a molecule of oxygen. This causes a transient increase in the chemical reactivity of the oxygen molecule, and converts it into a relatively strong oxidizing agent, singlet oxygen. It is the singlet oxygen that kills cells by causing lethal oxidative damage to biologically important structures.

A topical form of 5-ALA has been approved by the FDA for the photodynamic therapy (PDT) treatment of actinic keratoses 5-ALA (Levulan Kerastick Topical Solution, DUSA Pharmaceuticals New York, Inc. Valhalla NY 10595). According to the presumed mechanism of action, photosensitization following application of Levulan Topical Solution occurs through the metabolic conversion of 5-ALA to PpIX, which accumulates in the skin to which Levulan Topical Solution has been applied. When exposed to light of appropriate wavelength and energy, the accumulated PpIX produces a photodynamic reaction, a cytotoxic process dependent upon the simultaneous presence of light and oxygen. The absorption of light results in an excited state of the porphyrin molecule, and subsequent spin transfer from PpIX to molecular oxygen generating singlet oxygen, which can further react to form superoxide and hydroxyl radicals. Photosensitization of actinic (solar) keratosis lesions using the Levulan Kerastick, plus illumination with the BLU-U™ Blue Light Photodynamic Therapy Illuminator (BLU-U), is the basis for Levulan photodynamic therapy of skin lesions. It is presumed that the same mechanism could be utilized for photodynamic therapy of brain neoplasms using oral administration of 5-ALA, and this is the basis for future studies (but not this study).

It is the properties of the intracellular metabolism of 5-ALA, the subsequent intracellular accumulation of PpIX without extracellular spread, the selective and preferential accumulation of PpIX in neoplastic cells compared to normal cells and the fluorescent properties of the accumulated PpIX that form the basis for this proposal concerning the gross total resection of malignant brain tumors. The photodynamic therapy benefits of 5-ALA/PpIX in the treatment of malignant gliomas will likely be addressed in a subsequent proposal.

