4.1.2 Surgical Phase

5-ALA will be mixed in the minimum volume of sterile water or juice immediately before use and given as a single bolus orally approximately three hours prior to induction of anesthesia for surgical resection of a malignant brain tumor. Image-guided microsurgical resection of the tumor will be undertaken. The intensity of the white and blue light from the microscope will be measured at the shortest focal length of the microscope with a digital light meter before resection of the tumor is performed. During tumor resection under the surgical microscope, the tumor bed will be illuminated with deep blue light via a high pass optical filter in the microscopes light chain. The neurosurgeon will examine the tumor bed with a barrier filter in the optical chain of the surgical microscope (see Appendix B).

Under white light the neurosurgeon will take small biopsies from areas of obvious tumor and areas in the wall of the resection cavity that are judged to be normal (but possibly edematous), non-eloquent brain.

Under blue light, small biopsies will be taken from areas of strong fluorescence, weak fluorescence and non-fluorescing regions in the tumor resection cavity.

At all times, the neurosurgeon will use their best judgment to remove or biopsy only that tissue that would normally be removed or biopsied as part of any brain tumor procedure that was not involved or part of an investigational study.

Specimens will be collected regardless of fluorescence. All biopsy specimens, including those taken from the solid tumor, will be reviewed by a neuropathologist. Residual fluorescent tissue in the tumor cavity will be surgically removed only if in the judgment of the neurosurgeon these areas would have been resected using white light alone and that this would lead to a more complete resection of tumor. Pathologic confirmation of tumor type will be made by neuropathology.

After surgical resection of the tumor, the neurosurgeon will judge the extent of resection by estimating the volume of remaining obvious tumor seen under white light or fluorescent tissue seen under blue light.

Data Collection in Operating Room

Under White Light	Obvious Tumor	Obvious Normal Brain (possibly edemator		
Biopsy for Histology	A	В		
Tumor Content of Sample	X	X		
Specimen Labeled	X		X	
Under Blue Light	Strongly Fluorescent Tissue	Weakly Fluorescent Tissue	Non-Fluorescent Tissue	

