10. MEASUREMENT OF EFFECT

In this study, the study drug 5-ALA is not expected to have any direct effect on tumor cells. Future studies may be designed to investigate the potential of 5-ALA and its photosensitizing metabolite PpIX in a study of photodynamic therapy, but in this study no attempt will be made to photo-activate the tumor cells.

The study will look at the specificity and sensitivity of 5-ALA/PpIX for malignant glioma cells.

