11. REGULATORY AND REPORTING REQUIREMENTS

Adverse event (AE) reporting for this study is via the FDA safety information and adverse event reporting system, Medwatch, FDA form 3500A. The descriptions and grading scales found in the revised NCI Common Toxicity Criteria (CTC) version 3.0 will be utilized for adverse event reporting and are available in the Clinical Research Department and available on line at http://ctep.cancer.gov/reporting/ctc.html. Expected adverse events specific for 5-ALA are found below (Section 11.1.2).

- 11.1 Expedited Adverse Event Reporting (AE; formerly known as Adverse Drug Reaction)
 - 11.1.1 Expedited Reporting Guidelines Phase 1 studies with investigational agents (Including hospitalization defined in bullet 1 below)
 - For Hospitalization only Any medical event equivalent to CTC grade 3, 4, or 5 which precipitated hospitalization (or prolongation of existing hospitalization) must be reported regardless of designation as expected or unexpected and attribution.
 - The FDA safety information and adverse event reporting system, Medwatch,
 FDA form 3500A will be used for reporting within 24 hours.
- 11.1.2 Agent-Specific Expected Adverse Events List

The list below guides the investigator in determining which AEs require expedited reporting. Those AEs that do not require expedited reporting are reported in routine study data submissions.

- Skin reaction Grades 1 and 2.
- AST/ALT elevation Grades 1, 2, or 3.
- Nausea Grades 1 and 2.
- 11.1.3 Other Expected Adverse Events

For this protocol, the following more serious expected adverse events are risks associated with surgical removal of a malignant brain tumor and do not require expedited reporting:

- Adverse reaction to anesthesia Both local and general anesthesia involve risk. There is a possibility of complication or injury from all forms of anesthesia and sedation.
- Balance problems Difficulty with balance or vertigo may occur as a result of the tumor itself or from the surgery to correct it. Nausea and vomiting may also occur after surgery.
- Bleeding It is possible, though unusual, to experience an episode of bleeding, which may be extensive during or after surgery. Bleeding may

- require additional treatment or transfusion. Certain medications, such as antiinflammatory drugs, may increase the risk of bleeding.

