APPENDIX B

Ultraviolet-Illuminated Operating Room Microscope

Tumor Dye Project – Technical Aspects

5-aminolevulinic acid (5-ALA) – a naturally occurring non-fluorescing metabolic precursor, induces synthesis of protoporphyin IX (PpIX). PpIX fluoresces when exposed to the excitation light of blue-violet (wavelength 375-400nm.) It gives off a light with characteristic peaks 635 and 704nm. This is best viewed by filtering (440 long pass filter) out most other wavelengths except a small amount of excitation light.

The excitation light source is a 400 W short-arc Xe-lamp and a short pass filter (440nm.) integrated into a standard Leica surgical microscope. This filter can be switched on or off by the surgeon when needed. Light is delivered through a commercially available liquid light guide. The Leica OH series microscope is modified so that these filters can be switched on and off whenever the surgeon wishes to observe the fluorescence.

Two special filters for the 5-ALA fluorescence are used in a standard Leica OH microscope. The filters are a short pass (<440nm) filter which rotates in front of the microscope's standard 400-watt Xe light source. In addition, a special long pass (>440nm) barrier filter in the optical path allows clear viewing of the red fluorescence. Both filters are inserted and removed with one button on the microscope handle. With the push of that one button, the standard Leica OH microscope can then go back to being the neurosurgical and spine microscope it was designed for.

Using these modifications intraoperative detection of tumor fluorescence is possible without disturbing the routine of the surgical procedure. Switching between the two illumination modes does not require significant surgeon optical accommodation and does not interrupt the operation. All of these modifications are readily made to the standard neurosurgical microscope and requires no additional personnel in the operating room.

Appendix	С
Eligibility	Checklist

ppendix C ligibility Checklist	

Clinical/Radiological evidence of a primary malignant brain tumor	
Age ≥ 18 years old	
ECOG Performance Status ≤ 2	
Karnofsky ≥ 60%	
Leukocytes ≥ 3,000/mcL	
Absolute neutrophil count ≥ 1,500/mcL	
Total bilirubin within normal institutional limits	
AST (SGOT)/ALT(SGPT) ≤ 2.5 X institutional upper limit of normal	
Creatinine within normal institutional limits	
or Creatinine clearance ≥60mL/min/1.73 m ²	
Not pregnant	
Able to understand and sign informed consent	

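### Section 11.1.3 exempts brain injury, neurologic decline, paralysis and seizure from expedited reporting with no attribution condition, so a Grade 2-3 injury related to 5-ALA plus blue light could lose or delay its expedited report

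*Combined protocol and SAP*

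**What the plan says.** **Light and drug.** Section 2.1.2 states that "PpIX is strongly fluorescent when activated by light at the far blue end of the visible spectrum". For topical 5-ALA on skin, under light of suitable wavelength and energy, it adds that "the accumulated PpIX produces a photodynamic reaction, a cytotoxic process dependent upon the simultaneous presence of light and oxygen". It presumes that the same mechanism could be used in brain tumors, as a matter for later studies. In this trial, section 4.1.2 says that "the tumor bed will be illuminated with deep blue light". Appendix B gives an excitation band of 375-400 nm, from a 400 W xenon lamp behind a 440 nm short pass filter. Section 10 says that "in this study no attempt will be made to photo-activate the tumor cells".

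**Expected events.** Section 6.2 defines expected events as those listed in 11.1.2 and 11.1.3, and uses expectedness for expedited reporting only. Section 11.1.2, the agent-specific list, has three entries, each limited by grade: skin reaction, AST/ALT elevation and nausea. Section 11.1.3 lists brain injury, paralysis, neurologic decline and seizure, among others. It says that these events "are risks associated with surgical removal of a malignant brain tumor and do not require expedited reporting". It sets no grade limit and no attribution condition.

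**Light measurement.** Section 4.1.2 has white and blue light intensity measured with a light meter before resection. The data sheets in Appendix C have an intensity entry and a time entry for each biopsy sample. They have no entry for how long the blue light was on.

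**The concern.** Brain at the wall of the cavity receives both the drug's fluorescent metabolite and its excitation light. If that combination caused harm there, it would appear as a focal deficit, edema, a seizure or paralysis. These are signs that 11.1.3 already assigns to surgery. Because the list has no attribution condition, an event that the investigator rates Possible, Probable or Definite for 5-ALA can still count as expected, and its expedited report is then delayed or dropped.

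At stake is how quickly the FDA learns of a drug-related neurologic event in a trial whose first objective is a safe dose. A second, smaller matter is the evidence for attribution. Whoever judges causality has one intensity reading and no exposure time.

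**Working it through.** There is no sample size or error rate to recompute. The check sets the reporting rules side by side.

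**Step 1. What the expected label changes.** The rows are events rated Possible, Probable or Definite for 5-ALA.

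| Related event | 6.3.2 table, unexpected | 6.3.2 table, expected | Table closing 11.1.3, unexpected | Table closing 11.1.3, expected |
|---|---|---|---|---|
| Grade 2 | 10 calendar days | none | 10 working days | none |
| Grade 3, hospitalized | 24 hours, then 5 calendar days | 10 calendar days | phone in 24 hours, then 10 working days | none |
| Grade 3, not hospitalized | 24 hours, then 5 calendar days | none | phone in 24 hours, then 10 working days | none |
| Grade 4-5 | 24 hours, then 5 calendar days | same | phone in 24 hours, then 5 calendar days | same |

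The label matters at Grades 2 and 3 only. The two tables also disagree on an expected Grade 3 event with hospitalization: 10 calendar days in one, no expedited report in the other.

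**Step 2. Whether another clause restores the report.** Sections 6.3.1 and 11.1.1 require any Grade 3-5 event that causes or prolongs hospitalization to be reported, whatever its expectedness or attribution, with Medwatch used within 24 hours. That would cover the Grade 3 hospitalized row. However, the restatements after the 6.3.2 table and in 11.5 except protocol-specific reporting exclusions, and 11.1.3 can be read as one. Section 11.5 also has staff alert the DSMC at once to serious adverse events. It stops the study, with immediate reports to SCRIHS and the FDA, if such an event is found to be associated with the protocol. Expectedness plays no part there. A related Grade 2 event, or a Grade 3 event without hospitalization, that does not meet the seriousness definition in 11.5 has no such backstop.

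**Step 3. Whether dose escalation is affected.** Section 4.2 counts as dose-limiting any Grade 2 or higher event directly attributed to 5-ALA or its metabolites, and PpIX is a metabolite. Section 11.5 has the DSMC determine causality for each adverse event. Neither uses expectedness, so the label does not remove an attributed event from the escalation count. One consequence is that a related Grade 2 neurologic event can be dose-limiting and still need no expedited report.

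**Step 4. Whether tissue without tumor can carry PpIX.** Section 2.1.3 says that normal brain makes very little. In the European study summarized in section 2.3, 7 of 185 fluorescing biopsies contained no tumor cells (7/185 = 3.8%; the complement, 178/185 = 96.2%, matches the predictive value reported there). All seven fluoresced weakly. Exposure outside tumor is therefore limited but not excluded.

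**Step 5. Whether exposure can be derived.** Light exposure = intensity x time. Intensity is measured once, before resection. Illumination time is not collected, so exposure cannot be calculated for any patient. The documents give no cytotoxic threshold to compare it with.

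**The case against.** The strongest reply is that 11.1.3 is framed by cause. Its opening ties the listed events to surgical removal, and its brain-injury entry to the procedure, so a drug-plus-light injury arguably falls outside the list. Attribution is graded separately, causality is reviewed for every event, and all adverse events reach routine reporting. This stands in part, and it is why the misclassification is something that could happen, not something that must. But 6.2 makes an event expected by its being listed, and a postoperative deficit rarely shows its cause when the reporting clock starts.

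Several stronger readings are tempting, and the documents do not support them.

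- A reader might infer that section 10 denies photo-activation and so contradicts the plan. It says only that none will be attempted, which separates this trial from photodynamic therapy studies.
- A reader might infer that the microscope light is phototoxic. The cytotoxicity sentence concerns topical drug on skin and depends on wavelength and energy. The documents give no irradiance at the brain and no threshold. They report low PpIX in normal brain, and section 2.2.2 describes European use as safe.
- A reader might infer that light exposure goes unrecorded altogether. Intensity is measured; only duration is missing.
- A reader might infer that patients at one dose level differ many-fold in light exposure, or that cell kill distorts the survival analysis. No illumination times are given, so both are speculation.

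It is also fair to object that the 6.3.2 table treats expectedness and attribution as separate axes, and that a condition linking them will add reports for deficits that prove to be surgical. That is a real cost.

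**Conclusion.** The point holds as a gap in reporting rules, with a small gap in data capture. If a neurologic event on the 11.1.3 list is rated at least possibly related to 5-ALA, the 6.3.2 table drops the expedited report at Grade 2. At Grade 3 it lengthens the deadline from 24 hours plus 5 days to 10 days with hospitalization, and removes the report without it. The table closing 11.1.3 requires none for any expected Grade 1-3 event. Sections 6.3.1, 11.1.1 and 11.5 conflict with this, and the protocol does not say which governs.

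Grade 4-5 events are expedited either way, and dose escalation is not directly affected. The conclusion assumes that staff apply the list as 6.2 directs, by membership. It does not assume that the illumination causes injury, which the documents neither show nor rule out.

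**What to change.** 1. In 11.1.3, state that a listed event counts as expected only when its attribution to 5-ALA, including 5-ALA plus light, is Unlikely or Unrelated. Otherwise expectedness is judged by 11.1.2 alone.
2. Reconcile that sentence with 6.3.1, both reporting tables, 11.1.1 and 11.5, including whether 11.1.3 is one of the protocol-specific exclusions.
3. Add total blue-light minutes to the Intra-Operative Data Sheet, beside the intensity already measured, and give both to the DSMC at its cohort reviews.

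The cost is wording, one data field filled in by staff already in the room, and more expedited reports for postoperative deficits rated Possible. The documents do not allow that number to be estimated. No dose or treatment rule changes.
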